#### **2.2.3. Safety Endpoint**

The safety of DE-122 will be evaluated by:

- Adverse events (AEs)
- Slit lamp biomicroscopy
- IOP
- Indirect ophthalmoscopy

- Laboratory assessment including serum chemistry, hematology, and urinalysis
- Vital signs
- Electrocardiogram (EKG)

#### **2.2.4. Pharmacokinetics Endpoint**

Pharmacokinetic profile will be assessed by pharmacokinetic parameters including AUC,  $C_{max}$ ,  $t_{max}$ , and  $t_{1/2}$ .

#### **2.2.5. Immunogenicity Endpoint**

Immunogenicity will be assessed by the incidence of DE-122 antibody development in serum.

#### **2.2.6. Biomarker Endpoint**

For biomarker investigation, serum samples and aqueous humor samples from the study eye will be measured for levels of angiogenesis-related proteins.

#### **2.2.7. Exploratory Endpoints**

##### **2.2.7.1. M-CHARTS™**

The degree of metamorphopsia will be explored by vertical metamorphopsia score (VM) and horizontal metamorphopsia score (HM) from the M-CHARTS™.

##### **2.2.7.2. Swept Source OCT Angiography**

Swept Source OCT (SS-OCT) angiography will be evaluated for future exploratory research. This exploratory evaluation will be a collaboration between Santen and a third party, and is out of the scope of this document.

##### **2.2.7.3. Subretinal Hyper-Reflective Material and Retinal Pigment Epithelium Elevation**

Subretinal hyper-reflective material (SHRM) and retinal pigment epithelium elevation (RPEE) by SD-OCT will be evaluated for future exploratory research.

### 3. STUDY DESIGN

#### 3.1. General Study Design

This is a randomized, double masked and active controlled study assessing the safety and efficacy of repeated intravitreal injections of DE-122 (2.0 mg or 4.0 mg) in combination with Lucentis® compared to Lucentis® monotherapy in subjects with wet AMD. Seventy-six (76) subjects with wet AMD were randomly assigned to one of three treatment arms in two stages:

[figure not shown]
- Arm 1: Sham + Lucentis® 0.5 mg (N=17)
- Arm 2: DE-122, 2.0 mg + Lucentis® 0.5 mg (N=31)
- Arm 3: DE-122, 4.0 mg + Lucentis® 0.5 mg (N=28)

As shown in the Study Design Diagram ([Figure 1](#)), this study will consist of two stages. In Stage 1, the first 6 subjects will be randomized to either Arm 1 or Arm 2 in a 1:1 ratio. After all the 6 subjects have completed the Week 4 visit, the Safety Review Team will review the data to determine whether or not the safety and tolerability is acceptable. Subsequently in Stage 2, approximately 70 subjects will be randomized in a 1:2:2 ratios among the three arms.

Subjects will receive, in combination with Lucentis®, either 6 monthly intravitreal injections of DE-122 (2.0 mg), DE-122 (4.0 mg), or Sham in the study eye. The Primary Analysis is planned when all subjects complete the Week 24 visit. The Follow-up Analysis is planned at Week 32 to assess the number of anti-VEGF injections used for Rescue in addition to efficacy and safety data.

To be eligible, a subject must have been previously treated (i.e., At least 3 IVT injections of Anti-VEGF for treatment naïve eyes or eyes adequately maintained on continuous intravitreal anti-VEGF therapy). This condition was not required for subjects who enrolled before Protocol Amendment 06.

**Figure 1: Study Design Diagram**

### 3.2. Randomization and Masking

In Stage 1, the first 6 subjects will be randomized to either Arm 1 or Arm 2 in a 1:1 ratio. A blocked randomization with a fixed block size of 2 will be employed.

In Stage 2, approximately 70 subjects will be randomized to all three Arms in a 1:2:2 ratios. A blocked randomization with a fixed block size of 5 stratified by lesion type (polypoidal choroidal vasculopathy [PCV] vs. non-PCV) will be employed. Approximately one third (1/3) of the subjects in each arm are expected to have PCV in Stage 2.

This is a double-masked study, where the subjects and the examiners including the Principal Investigator (PI), are masked to the treatment regimen. However, the designated injecting physician (who is not the PI) will not be masked to the treatment regimen.

The Sponsor will have masked and unmasked data review teams. The designated Safety Review Team will review the safety data of the 6 subjects in Stage 1 to determine if the safety and tolerability of the doses at Week 4 are acceptable. In case of a medical emergency, the Principal

Investigator or site staff may reveal the treatment information by unmasking in the Interactive Web Response Systems (IWRS).

### **3.3. Sample Size Planning**

Approximately 76 subjects (Arm 1: 17, Arm 2: 31, Arm 3: 28) with wet AMD will be enrolled at approximately 14 sites. The sample size is not based upon any statistical considerations.

### **3.4. Visits and Assessments**

Assessments at each visit and visit windows are specified in the Schedule of Event ([Table 1](#)).

**Table 1: Schedule of Events**

**\*Only the subjects who have consented under the protocol prior to Amendment 07 require the grayed-out examinations in the table.**

Visit Number	Visit 0 (SCRN)	Visit 1	Visit 2	Visit 3	Visit 4	Visit 5	Visit 6	Visit 7	Visit 8	Visit 9	Visit 10	Visit 11	Visit 12	Visit 13 /Exit
Visit Schedule (Time window; days)	D-14 to -1	D1	D3	W1	W4	W8	W12	W16	W20	W20 + 2 days	W20 + 7 days	W24	W28	W32
			D3	D8 (±1)	D29 (±3)	D57 (±3)	D85 (±4)	D113 (±4)	D141 (±4)	W20 + 2 days	W20 + 7(±1) days	D169 (±5)	D197 (±5)	D225 (±5)
Informed consent a	X													
Demographics/Eligibility	X													
Medical/surgical history, Concomitant medication	X	X	X	X	X	X	X	X	X	X	X	X	X	X
Physical examination	X											X		X
Vital signs	X	X		X	X	X	X	X	X			X	X	X
EKG	X			X							X	X		X
BCVA (ETDRS)	X	X		X	X	X	X	X	X			X	X	X
M-CHARTS™	X	X		X	X	X	X	X	X			X	X	X
Slit-lamp biomicroscopy b	X	X		X	X	X	X	X	X			X	X	X
Intraocular pressure (IOP) c	X	X		X	X	X	X	X	X			X	X	X
Indirect ophthalmoscopy b	X	X		X	X	X	X	X	X			X	X	X
SD-OCT	X	X		X	X	X	X	X	X			X	X	X
SS-OCT angiography d	X	X		X	X	X	X	X	X			X	X	X

**Table 1: Schedule of Events (Continued)**

Visit Number	Visit 0 (SCRN)	Visit 1	Visit 2	Visit 3	Visit 4	Visit 5	Visit 6	Visit 7	Visit 8	Visit 9	Visit 10	Visit 11	Visit 12	Visit 13 /Exit
Visit Schedule (Time window; days)	D-14 to -1	D1	D3	W1	W4	W8	W12	W16	W20	W20 + 2 days	W20 + 7 days	W24	W28	W32
			D3	D8 (±1)	D29 (±3)	D57 (±3)	D85 (±4)	D113 (±4)	D141 (±4)	W20 + 2 days	W20 + 7(±1) days	D169 (±5)	D197 (±5)	D225 (±5)
Fundus photography (FP)	X				X		X					X		X
Fluorescein angiography (FA)	X				X		X					X		X
Urine pregnancy test e		X												
Urinalysis f	X				X		X					X		X
Serum pregnancy test e	X											X		X
Hematology, chemistry serum sample f	X				X		X					X		X
PK serum sample g		X	X	X	X				X	X	X	X		
Biomarker serum sample g		X	X	X	X				X	X	X	X		
Immunogenicity serum sample		X										X		
Pharmacogenomics/genomics blood sample a, h		X												
Biomarker aqueous humor sample a		X			X				X					

**Table 1: Schedule of Events (Continued)**

Visit Number	Visit 0 (SCRN)	Visit 1	Visit 2	Visit 3	Visit 4	Visit 5	Visit 6	Visit 7	Visit 8	Visit 9	Visit 10	Visit 11	Visit 12	Visit 13 /Exit
Visit Schedule (Time window; days)	D-14 to -1	D1	D3	W1	W4	W8	W12	W16	W20	W20 + 2 days	W20 + 7 days	W24	W28	W32
			D3	D8 (±1)	D29 (±3)	D57 (±3)	D85 (±4)	D113 (±4)	D141 (±4)	W20 + 2 days	W20 + 7(±1) days	D169 (±5)	D197 (±5)	D225 (±5)
Lucentis® IVT injection 		X			X	X	X	X	X					
DE-122 or Sham IVT Injection 		X			X	X	X	X	X					
Adverse event		X	X	X	X	X	X	X	X	X	X	X	X	X

SCRN= Screening; D=Day; W=Week; PK=Pharmacokinetic

- a. Collection and Pharmacogenomics/genomics blood sample collection.
- b. On days when either Lucentis®/DE-122 or Lucentis®/Sham IVT injections are administered, slit lamp biomicroscopy and indirect ophthalmoscopy will be performed prior to injection and within 30 minutes after DE-122 or Sham injection. This will be also applied for the post IVT injection of Rescue treatment.
- c. On days when either Lucentis®/DE-122 or Lucentis® /Sham IVT injections are administered, IOP will be performed before and after Lucentis® IVT injection. In addition, after DE-122 or Sham injection, IOP will be performed again. This will be also applied for the post injection of Rescue treatment.
- d. Selected sites will conduct.
- e. Serum and urine pregnancy tests are to be performed on all females of child-bearing potential.
- f. Subjects should fast for a minimum of 8 hours prior to urine specimen and blood draw for serum chemistry tests.
- g. At baseline (Day 1, Visit 1), serum sample for DE-122 concentration (if applicable) and biomarker will be collected
- 1) prior to the Lucentis® injection;
  - 2) post DE-122 or Sham injection: 3 hours, 48 hours, 1 week and 4 weeks (prior to the Lucentis® injection).
- At Week 20, serum sample for DE-122 concentration (if applicable) and biomarker will also be collected
- 1) prior to the Lucentis® injection;
  - 2) post DE-122 or Sham injection: 3 hours, 48 hours, 1 week and 4 weeks.
- h. Pharmacogenomics/genomics blood sample can be drawn once at Day 1 or any visit after Visit 1(Day 1) during the study.
- i. Lucentis® will be administered first, and then DE-122 or Sham will be injected. Rescue treatment with any anti-VEGF IVT injection can be performed during the Week 24 and Week 28 visits.

## 4. DEFINITIONS

### 4.1. Time-Related Terms

#### 4.1.1. Screening Visit

The screening visit is Visit 0 when the subject provided written informed consent.

#### 4.1.2. Baseline Visit

The *baseline visit* is Visit 1 (Day 1) visit when the subject is randomized.

#### 4.1.3. Study Day

The *study day* variable is the relative day of the observation with respect to the reference date, which is set to Day 1. In this study, the reference date is the baseline visit date, and the study day will be defined as:

- For days prior to the injection date, study day = date – baseline visit date
- For days on/after the injection date, study day = date – baseline visit date + 1

Note that there is no study day 0.

#### 4.1.4. Analysis Periods

Analysis periods for the efficacy and safety analysis are defined in [Table 2](#).

**Table 2: Analysis Periods**

Analysis Period	Analysis Period Start Date	Analysis Period End Date
On-treatment Period	The date of the first Lucentis® injection	The date of the Week 24 visit, or the Study Exit date, whichever came first
Follow-up Period	The date of the first day after Week 24 visit	The Study Exit date
Entire Study	Efficacy: the date of randomization; Safety: the date of the first Lucentis® injection	The Study Exit date

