**Table 3: Post-Baseline Analysis Visit and Analysis Window**

Post-Baseline Analysis Visit (Target Assessment Date)	Visit Window	Analysis Window
Week 1 (Day 8)	[7, 9]	[2, 18]
Week 4 (Day 29)	[26, 32]	[19, 43]
Week 8 (Day 57)	[54, 60]	[44, 71]
Week 12 (Day 85)	[81, 89]	[72, 99]
Week 16 (Day 113)	[109, 117]	[100, 127]
Week 20 (Day 141)	[137, 145]	[128, 155]
Week 24 (Day 169)	[164, 174]	[156, 183]
Week 28 (Day 197)	[192, 202]	[184, 211]
Week 32 (Day 225)	[220, 230]	[212, 253]

For analyses involving post-baseline visits, if there are two or more measurements that fall into the same analysis window of a post-baseline visit, then the measurement at visit with any injection will be selected. If there is no visit with any injection, then the measurement closest to the target assessment day will be selected for that visit. In the case that two measurements are equidistant to the target assessment day, i.e., one is before and one is after the target assessment day, the later one will be selected for that visit.

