### 4.3. Safety-Related Definitions

#### 4.3.1. Adverse Event

An AE is any untoward medical occurrence in a subject administered a pharmaceutical product and which does not necessarily have a causal relationship with the study drug(s).

An on-study AE can occur at any time after the date of informed consent through the last study visit. An AE will be considered as treatment-emergent if the AE onset occurs on or after the analysis period start date and prior to or on the on-treatment analysis period end date as defined in [Section 4.1.4](#). Treatment-emergent AEs are a subset of on-study AEs. Both on-study and treatment-emergent AEs are to be recorded, but only treatment-emergent AEs will be tabulated.

Each AE will be classified into a system organ class (SOC) and coded to a preferred term (PT) using Medical Dictionary for Regulatory Activities (MedDRA), version 20.0 published in 2017.

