### **9.1. Adverse Event**

Subjects with any AE(s), SAE(s), SAR(s), serious SAR(s) and ESI(s) will be tabulated for each actual treatment received. Besides the overall AE summary, subjects with any AE(s) will be tabulated by SOC and PT specified in MedDRA Version 20.0. Subjects with any AE(s) will also be tabulated by SOC, PT and maximum severity. A subject who experienced multiple AEs within a SOC or PT will be counted only once at the maximum severity for that SOC or PT. SAEs, SARs, and Serious SARs will be tabulated similarly.

Summaries for ocular AEs and non-ocular AEs will also be performed. Ocular AEs, ocular SAEs and ocular SARs will be summarized for study eyes and fellow eyes separately. Any ocular AE that occurred simultaneously to both eyes will be counted once for both the study eye and the fellow eye.

All AE tabulations will be performed on the Safety population for the On-treatment period, Follow-up period and entire study.

AEs, AEs leading to death, AEs leading to discontinuation, SAEs, and ESIs, if any, will be listed separately.

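### SAP Table 2 has no On-treatment end date for a subject who misses Week 24 but stays in the study, so follow-up adverse events count as treatment-emergent (low severity)

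*SAP*

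**What the plan says.** SAP 4.1.4, Table 2, starts the On-treatment period at "The date of the first Lucentis® injection" and ends it at "The date of the Week 24 visit, or the Study Exit date, whichever came first". The Follow-up period starts at "The date of the first day after Week 24 visit" and ends at Study Exit. Neither row says what to do when there is no Week 24 visit.

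SAP 4.3.1 carries this end date into the definition of a treatment-emergent event: "AE onset occurs on or after the analysis period start date and prior to or on the on-treatment analysis period end date". It sets no limit relative to the last injection and no cut at rescue. The same section adds that "only treatment-emergent AEs will be tabulated".

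SAP 9.1 says: "All AE tabulations will be performed on the Safety population for the On-treatment period, Follow-up period and entire study".

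SAP Table 3 places Week 24 at Day 169, with a visit window of Days 164 to 174 and an analysis window of Days 156 to 183. Week 28 is Day 197 (192 to 202) and Week 32, the exit visit, is Day 225 (220 to 230). The last scheduled study injection is at Week 20, Day 141 (137 to 145). Rescue with any anti-VEGF injection is possible at Weeks 24 and 28 (SAP 4.3.3 and Table 1, footnote i).

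**The concern.** The Table 2 rule works for a subject who attends Week 24 and for one who leaves the study before it. It does not work for a subject who misses Week 24 and then returns at Week 28 or Week 32. For that subject Study Exit is the only date left, so the On-treatment period takes in the whole follow-up phase and the Follow-up period cannot be derived.

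An illustration: last study injection on Day 141, no Week 24 visit, rescue at Week 28 (Day 197), an ocular event on Day 200, exit on Day 225. As written, the event is a treatment-emergent event of the randomised arm, although it followed a rescue injection in the follow-up phase. The same event in a subject who attended Week 24 would fall in Follow-up.

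Safety is part of the primary objective (SAP 2.1), and the adverse event tables are split by these periods. For BCVA the SAP censors Week 28 and Week 32 records after rescue (SAP 8.1.1); there is no matching rule for adverse events.

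**Working it through.** **1. Do other rules supply the missing date?** No.
- The analysis windows in SAP 4.1.5 map measurements to visits. They do not create a visit date. If the Week 24 visit in Table 2 is read as the analysis visit, a subject with no visit on Days 156 to 183 still has no date.
- The imputation rules in SAP 6.2 cover event and medication dates, not visit dates.
- The Study Exit term settles only the case of a subject who leaves before Week 24.

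**2. Reproduce the plan's dates.** Target day = 7 × week + 1.
- Week 20: 141; Week 24: 169; Week 28: 197; Week 32: 225.
- Adding and subtracting the Table 1 windows gives every visit window in SAP Table 3.

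**3. Length of the On-treatment period.**
- Week 24 attended: ends Day 169, which is 169 − 141 = 28 days after the Week 20 injection (19 to 37 over the visit windows).
- Week 24 missed, exit at Week 32: ends Day 225, which is 225 − 141 = 84 days after that injection (75 to 93).
- Difference: 225 − 169 = 56 days, or 56/169 = 33%. Over the windows: 220 − 174 = 46 to 230 − 164 = 66 days.
- After a Week 28 rescue: 225 − 197 = 28 days (220 − 202 = 18 to 230 − 192 = 38) count as on-treatment.

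**4. Largest effect of one subject on an adverse event row** (arm sizes 17, 31 and 28 from SAP 3.1).
- Arm 1: 1/17 = 5.9 points. Arm 2: 1/31 = 3.2. Arm 3: 1/28 = 3.6.
- SAP 9.1 counts a subject once per system organ class or preferred term, so this maximum needs the event to occur first in the extra days.

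**5. Expected effect** (assumption: constant hazard). If a subject's on-treatment incidence to Day 169 is p, to Day 225 it is 1 − (1 − p)^(225/169).
- p = 30% becomes 37.8% (+7.8 points); 50% becomes 60.3% (+10.3); 70% becomes 79.9% (+9.9).
- Per affected subject the arm-level shift is therefore 7.8/17 to 10.3/17 = 0.46 to 0.61 points in Arm 1, 0.25 to 0.33 in Arm 2 and 0.28 to 0.37 in Arm 3.

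**6. How many subjects?** The documents give no rate. If 2% to 5% miss Week 24 and continue (assumed), that is 76 × 0.02 = 1.5 to 76 × 0.05 = 3.8 subjects. The expected arm-level shift is then 0.02 × 7.8 = 0.16 to 0.05 × 10.3 = 0.52 points.

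**7. SAP 4.3.1 beside 9.1.** If only treatment-emergent events are tabulated and these end with the On-treatment period, the Follow-up table promised in 9.1 is empty for every subject. The two sections cannot both be followed literally.

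**The case against.** The strongest reply is that this is a narrow drafting gap. It needs a subject who misses Week 24 and stays in the study. If Table 2 is read through the analysis visits, it needs no visit at all during Days 156 to 183. No event is lost: the entire-study period in Table 2 does not depend on the Week 24 visit, and adverse events, serious events and events of special interest are listed. The error attributes more events to study treatment, not fewer. The trial is descriptive, with no hypothesis tested (Protocol 16.2.2). The constant hazard is also doubtful for ocular events. In the earlier phase I/II study the most common event was attributed to the injection procedure (Protocol 5), and no study injection is scheduled after Week 20. All of this stands and limits the size. It does not supply the missing date.

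A reader might infer four stronger things that the documents do not support.
- That the missed visit is what makes events after early stopping of study drug treatment-emergent. Such events count up to Week 24 even when that visit is attended; only the part beyond Week 24 is due to this gap.
- That no subject who missed Week 24 can be classified at the Week 24 analysis. Enrolment is staggered, so most would already have an exit date by then. Only a late-enrolled subject who has not yet exited lacks both dates.
- That the arms become unequal. This needs missed visits to differ by arm, for which there is no evidence.
- That contributing nothing to the Follow-up table is peculiar to these subjects. Under a literal reading of SAP 4.3.1 it holds for everyone.

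**Conclusion.** The gap is real and of low severity. Applied as written, Table 2 gives a subject who misses Week 24 but continues an On-treatment period about 56 days too long and no Follow-up start, and SAP 4.3.1 then classes that subject's follow-up events, including those after a Week 28 rescue, as treatment-emergent. The dates follow from the SAP alone.

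The effect on the tables depends on a count that the documents do not give. The single-subject shifts in step 4 are upper limits. The expected shift is well under 1 point, given either one affected subject per arm or a missed-visit rate of 2% to 5%, with a constant hazard. The case for correcting it is that the derivation is otherwise left to the programmer and the remedy is nearly free. The conflict between SAP 4.3.1 and 9.1 sits in the same definition, does not depend on a missed visit and touches every subject.

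**What to change.** In SAP Table 2, define the On-treatment end as the earliest of the Week 24 visit date, the Study Exit date and Day 183, the upper limit of the SAP's own Week 24 analysis window. Start Follow-up on the next day for every subject still in the study. Every subject then has a derivable date, including at the Week 24 analysis. For a subject who misses Week 24, 225 − 183 = 42 of the 56 extra days move to Follow-up, and every rescue given within the Week 28 visit window (Days 192 to 202) falls there too.

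In the same edit, reconcile SAP 4.3.1 with 9.1 by stating which adverse events enter the Follow-up and entire-study tables.

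The cost is SAP wording and one line in the derivation of the adverse event dataset, with no new data. There are two small downsides. A subject who misses Week 24 keeps up to 183 − 169 = 14 more on-treatment days than one who attends on Day 169, and a Week 24 visit held after Day 183 no longer extends the period.

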#### 4.1.5. Out-of-Window Measurements, Analysis Window and Analysis Visit

A measurement collected at a visit is an out-of-window measurement if the study day of the visit falls outside of a visit window specified in [Table 1](#), or a within-window measurement otherwise.

Analysis visit is a timing variable which will be used for all analyses involving visits. For each analysis visit, an analysis window is provided in order to determine which of the analysis visit a measurement should be mapped to. The analysis visit of a measurement will be determined by the study day of the measurement and the specified analysis windows. The study visit, assigned when the measurement was collected, will not necessarily agree with the analysis visit.

The following analysis windows for post-baseline visits will be applied to minimize the amount of missing data for analysis purposes:

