23.4.20. Procedure for Biomarker Serum Sample

Approximately 10 mL of blood sample will be collected for biomarker analysis from the subject pre Lucentis® injection at Visit 1 (Day 1), 3 hrs (\pm 10 mins) post DE-122 or Sham injection at Visit 1 (Day 1), Visit 2 (Day 3) if applicable, Visit 3 (Week 1), Visit 4 (Week 4), pre Lucentis® injection at Visit 8 (Week 20), 3 hrs (\pm 10 mins) post DE-122 or Sham injection at Visit 8 (Week 20), Visit 9 (Week 20 + 2 days) if applicable, Visit 10 (Week 20 + 7 days) and Visit 11 (Week 24).

There will be up to approximately 10 blood draws for Biomarker. The total amount of blood collected from each subject during this study will be up to approximately 100 mL.

Refer to the separate procedure manual for sample handling, storage, and shipment.

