#### 4.3.5. Change and Percent Change from Baseline

The *change and the percent change from baseline* in a measure at a post-baseline visit will be defined as:

- Change = score at the post-baseline visit – baseline score.
- Percent change from baseline =  $100 \times \text{change} / (\text{baseline score})$

For any measure assessed pre and post injection at visits with injection(s), only the pre-injection scores at the visit will be used to derive the change-from-baseline variable.

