## 12. BIOMARKER ANALYSIS

Translational Research will provide the report of biomarker investigation. Scores, changes from baseline and percent change from baseline in levels of potential biomarkers will be summarized descriptively by actual treatment received and analysis visit. Besides the summary tables, plots of biomarker measures versus analysis visit will be provided. Pearson's correlation between change from baseline in BCVA and each biomarker will be analyzed by actual treatment and analysis visit. The 95% confidence interval of the correlation coefficient based on Fisher's Z transformation will be provided.

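### SAP Table 3 and its one-value-per-window rule keep only 4 of 9 (or 4 of 7) post-baseline serum biomarker draws in the planned summaries

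*SAP*

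**What the plan says.** Protocol 23.4.20 lists the serum draws: before Lucentis and at 3 hours on Day 1, then Visit 2 (Day 3), Visit 3 (Week 1) and Visit 4 (Week 4); before Lucentis and at 3 hours at Visit 8 (Week 20), then Visit 9 (2 days later), Visit 10 (7 days later) and Visit 11 (Week 24). It adds: "There will be up to approximately 10 blood draws for Biomarker". Footnote g of SAP Table 1 shows the intent, with sampling "post DE-122 or Sham injection: 3 hours, 48 hours, 1 week and 4 weeks" for both the Day 1 and the Week 20 doses. Visits 2 and 9 take place only for subjects who consented before Version 4.0 (Protocol 7.5.2.2 and 7.5.2.9).

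SAP 12 says that biomarker scores and changes from baseline "will be summarized descriptively by actual treatment received and analysis visit". The plots and the correlations with BCVA change are also by analysis visit. SAP 4.1.5 makes the analysis visit depend on study day and not on the nominal visit, and applies it generally: "Analysis visit is a timing variable which will be used for all analyses involving visits". Table 3 provides post-baseline windows for Weeks 1, 4, 8, 12, 16, 20, 24, 28 and 32 only. A selection rule follows it for the case "if there are two or more measurements that fall into the same analysis window of a post-baseline visit". A measurement from an injection visit is preferred; failing that, the one nearest the target day; and if two lie equally far on either side of the target, the later one.

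**The concern.** Table 3 suits measures taken once per monthly visit. The biomarker serum series is a different design: several draws within a week of two injections, meant to show what happens soon after dosing. Under a rule that keeps one value per window of several weeks, most of that early course cannot appear in a table or plot. Evaluating biomarkers after repeated injections is a secondary objective in both documents (Protocol 6, SAP 2.1), and Visits 2 and 9 consist of blood draws plus adverse-event and medication updates.

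The SAP avoids this problem for PK, which is sampled at the same times: SAP 4.4.2 estimates PK parameters over two intervals (Day 1 to Week 4, Week 20 to Week 24). No corresponding provision exists for biomarkers. At stake is whether an early change in angiogenesis-related proteins after the first or sixth dose would be visible in the planned output.

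**Working it through.** **Inputs.** Draw schedule and volume: Protocol 23.4.20. Visit windows: SAP Table 1. Analysis windows and selection rule: SAP Table 3 and the paragraph after it. Baseline: the last value before the first injection (SAP 4.2.2).

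**The plan's own figure.** Day 1 series: pre-dose, 3 h, Visit 2, Visit 3, Visit 4 = 5. Week 20 series: pre-dose, 3 h, Visit 9, Visit 10, Visit 11 = 5. Total 5 + 5 = 10 draws, and 10 × 10 mL = 100 mL. Both agree with Protocol 23.4.20. One draw is the baseline, so 10 − 1 = 9 are post-baseline. Without Visits 2 and 9, 9 − 2 = 7.

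**Mapping, with all visits inside their visit windows.**

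| Draw | Study day | Table 3 window | Outcome |
|---|---|---|---|
| Day 1, 3 h | 1 | none (first window starts on Day 2) | not summarised |
| Visit 2 | 3 | Week 1 [2, 18] | loses to Visit 3 |
| Visit 3 | 7–9 | Week 1 [2, 18] | kept |
| Visit 4 | 26–32 | Week 4 [19, 43] | kept |
| Visit 8, pre-dose | 137–145 | Week 20 [128, 155] | one of these |
| Visit 8, 3 h | 137–145 | Week 20 [128, 155] | two is kept |
| Visit 9 | 139–147 | Week 20 [128, 155] | loses to Visit 8 |
| Visit 10 | 143–153 | Week 20 [128, 155] | loses to Visit 8 |
| Visit 11 | 164–174 | Week 24 [156, 183] | kept |

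**Week 1.** No injection visit falls in this window, so distance from Day 8 decides. Day 3 is 8 − 3 = 5 days away; Visit 3 is at most 1 day away.

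**Week 20.** Visit 10 is 6 to 8 days after Visit 8, so it falls between Day 137 + 6 = 143 and Day 145 + 8 = 153, always inside the window. Visit 8 is the injection visit, so Visits 9 and 10 are set aside. Its two draws share a study day. The tie-break concerns values on opposite sides of the target day, so it does not choose between them.

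**Count.** Kept: Week 1, Week 4, one Week 20 value, Week 24 = 4. Consented before Version 4.0: 9 − 4 = 5 of 9 (56%) not summarised. Later subjects: 7 − 4 = 3 of 7 (43%). For the full schedule, the result is the same for every in-window combination of dates for Visits 3, 4, 8, 10 and 11: 3 × 7 × 9 × 3 × 11 = 6,237 combinations.

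**Off-schedule cases.** A Visit 3 draw on Day 13 ties with Day 3 (5 days each) and wins as the later. If it is taken on Days 14 to 18, or is missing, the Day 3 sample is reported as Week 1. If the Visit 8 draws are missing, a Visit 9 or Visit 10 sample is reported as Week 20. A 48-hour or 7-day sample can then share a row with samples taken at a different time from dosing.

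**The case against.** The strongest reply is that this is exploratory work with no hypothesis test, that SAP 12 assigns a biomarker report to a separate group which may use nominal times, and that nothing collected is destroyed. Parts of this stand. Listings are planned (SAP 6, Protocol 16.2) and serum is stored for future research (Protocol 15.1.1), so it would be wrong to infer that the results are never reported or the blood is wasted. The separate report is not a full answer: SAP 12 itself puts the summaries on analysis visit and offers no other time axis.

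A reader might also draw stronger conclusions that the documents do not support:

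- *That Table 3 has no place for any of these samples.* Only the Day 1 3-hour draw lacks a window. The others have one and are lost in selection.
- *That the Week 20 value is a pre-dose trough.* The rule that "only the pre-injection scores at the visit will be used to derive the change-from-baseline variable" sits in SAP 4.3.5, under safety definitions, and concerns change from baseline only. If it were read across to biomarkers, so would SAP 4.3.6, which defines a post-injection change that SAP 12 never requests. The choice of Week 20 value is unspecified.
- *That the first week after the sixth dose is lost in every subject.* Missing Visit 8 draws let a Visit 9 or 10 sample through, and the 3-hour value might be the one chosen.
- *That the BCVA correlations lose data.* BCVA is not measured at Visits 2, 9 or 10 (Protocol 23.4.5), nor scheduled after injection on Day 1 or at Week 20. No same-time BCVA exists to pair with the omitted draws.

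**Conclusion.** The point holds for serum biomarker tables and plots. They keep 4 of 9 post-baseline draws for subjects who consented before Version 4.0 and 4 of 7 for later subjects. The documents do not give the split between these groups, so no single study-wide percentage can be stated. The cause is the combination of the Table 3 windows and the selection rule.

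The counts assume that all draws are taken, that all visits are in window, and that exactly one value is kept per window, as the selection rule reads. Two further defects follow: the SAP does not identify which Visit 8 value represents Week 20, and off-schedule subjects can contribute samples taken at a different interval from dosing under the same label.

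The optional aqueous samples are unaffected, since the post-baseline ones (Visits 4 and 8) map to Weeks 4 and 20. PK is unaffected because it uses intervals. No efficacy or safety conclusion changes. The point still deserves correction, because a stated rule removes from the summaries much of the time course that the sampling was designed to capture for a secondary objective.

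**What to change.** In SAP 12 and 4.1.5, exempt biomarker serum from Table 3 and summarise and plot it by nominal sampling time: Day 1 pre-dose (baseline), Day 1 3 h, 48 h, Week 1, Week 4, Week 20 pre-dose, Week 20 3 h, Week 20 48 h, Week 20 + 7 days, and Week 24. Give change from baseline at each post-baseline time. State that the pre-injection-only rule in SAP 4.3.5 does not apply to these samples. Keep the BCVA correlation at visits where BCVA is also measured, and name the pre-injection biomarker value as the one used at Week 20.

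All 9 of 9, or 7 of 7, scheduled post-baseline draws would then enter the summaries. The cost is a few lines of SAP text and five more rows per table (10 time points instead of baseline plus 4), with no new samples or visits. The drawback is a smaller n at 48 hours, because only subjects who consented before Version 4.0 have those draws. Each row should show its n.
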